4.11.2. Secondary efficacy endpoints

No correction for multiple comparisons are planned for secondary endpoints.

Proportion of subjects with DAS28-CRP remission (score < 2.6) in each study arm will be presented at any time as well as at Day 29, Day 57, Day 85 and Day 113. Proportion of subjects will be presented together with confidence intervals, difference from placebo with confidence interval and p value for comparison vs. placebo calculated using proportion test. Logistic regression model will be prepared to explain achievement of response at any time with following factors: treatment (placebo will be the reference value), country (Ukraine will be the reference value) and baseline DAS28-CRP score. Moreover, descriptive statistics for time to remission will be presented along with median time to remission estimated using Kaplan-Meier method. Each treatment arm will be compared to placebo using log-rank test.

Change from baseline in the Tender/Painful and Swollen Joint Count as well as change from baseline in PhGA will be analyzed using MMRM and performed as described for primary endpoint.

All of patient reported outcomes - change from baseline in PAAP, PtGA, HAQ-DI, SF-36 and FACIT-F will be only presented descriptively for each timepoint.

American College Rheumatology (ACR)20, ACR50, ACR70 and ACR90 responder rates will be presented in form of percentage of subjects that meets the criteria for the endpoint alongside 95% confidence interval calculated using Wilsons' method. Difference between CPL409116 arms and placebo will be presented together with confidence interval and p value calculated using proportion test. Logistic regression model will be prepared similar to the previously described endpoint of DAS28-CRP remission.

Supportive analysis will be performed on PP population, as well as ITT with imputation based on last observation carried forward (LOCF) for continuous variables and NRI method for binary endpoints and performed as described for the ITT population.

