#### **10.9. Patient Reported Outcomes**

Change from baseline in:

- Patient's Assessment of Arthritis Pain (PAAP) VAS;
- Patient's Global Assessment of Arthritis (PtGA, VAS);
- Health Assessment Questionnaire – Disability Index (HAQ-DI);
- SF-36 RAND questionnaire;
- FACIT-F

will be presented descriptively for each timepoint. Description of additional analyses will be provided in the SAP.

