2.1.2. Secondary objectives

Efficacy:

[figure not shown]
- To determine the effect of CPL409116 at 3 different doses, compared to placebo in subjects with rheumatoid arthritis.
- To assess dose-response and exposure- response relationship for CPL409116.

Safety:

- To evaluate safety and tolerability of CPL409116 administered at doses: 60 mg, 120 mg or 240 mg twice a day for 12 weeks in subjects with RA.

Pharmacokinetics:

- To evaluate pharmacokinetic (PK) parameters for CPL409116 and metabolite M3 in patients with RA.

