2.1.2. Secondary endpoints

Clinical Efficacy:

- Proportion of subjects with DAS28-CRP remission at Weeks 4; 8; 12 and 16.
- American College of Rheumatology (ACR)20, ACR 50, ACR 70, and ACR 90 responder rates (Weeks 4, 8 and 12).
- Change from Baseline in the Tender/Painful and Swollen Joint Count (Weeks 4, 8 and 12).
- Change from Baseline in the Physician's Global Assessment (PhGA) of Arthritis (Weeks 4, 8 and 12).

Patient Reported Outcome:

- Change from baseline in the Patient's Assessment of Arthritis Pain (PAAP) VAS and Patient Global Assessment of Arthritis (PtGA, VAS) at Week 4, 8, and 12.
- Change from baseline in the Health Assessment Questionnaire – Disability Index (HAQ-DI) at Week 4, 8, and 12.
- Change from baseline in the SF-36 RAND 8 Domain scores and Physical Component Score (PCS) and Mental component score (MCS) at Week 12.
- Change from baseline in the Functional Assessment of Chronic Illness Therapy Fatigue (FACIT-F) total score at Week 12.

Safety:

Safety and tolerability of CPL409116: vital signs (blood pressure (BP), pulse and temperature), laboratory tests, Adverse Events (AEs) and Serious Adverse Events (SAEs), 12-lead electrocardiogram (ECG):

- Incidence and severity of adverse events, serious adverse events, and withdrawals due to adverse events (Baseline through Week 16).
- Incidence of abnormality in clinical chemistry parameters (Baseline through Week 16).
- Incidence of abnormality in haematological parameters (Baseline through Week 16).
- Change from baseline in blood pressure measurement (Baseline through Week 16).
- Change from baseline in pulse rate measurement (Baseline through Week 16).
- Change from baseline in temperature measurement (Baseline through Week 16).
- Incidences of targeted medical adverse events (Baseline through Week 16).

Pharmacokinetics:

- CPL409116 and metabolite M3 pharmacokinetic variables: $AUC_{(0-6h)}$, C_{max} , T_{max} , $T_{1/2}$ (if possible) and K_{el} (if possible) determined on Day 1, 8, 57 and 85.
- CPL409116 pharmacokinetic variables: C_{0h} , $C_{2.5h}$ determined on Day 29.

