4.11.1. Primary efficacy endpoints

The main analysis will be based on ITT population with supportive analyses using PP population data and imputed ITT population as sensitivity analysis.

In order to evaluate clinical efficacy of CPL409116 at week 12 in subjects with active RA who have had an inadequate response to methotrexate a Mixed Model for Repeated Measure (MMRM) will be prepared.

A set of hypotheses (H_0 – null and H_A – alternative) will be tested, one for each dose level of CPL409116.

H_01 : The mean change at week 12 from baseline in CPL409116 at dose of 60 mg BID is the same as that observed in placebo arm.

H_A1 : The mean change at week 12 from baseline in CPL409116 at dose of 60 mg BID is different from that observed in the placebo arm.

H_02 : The mean change at week 12 from baseline in CPL409116 at dose of 120 mg BID is the same as that observed in placebo arm.

H_A2 : The mean change at week 12 from baseline in CPL409116 at dose of 120 mg BID is different from that observed in the placebo arm.

H_03 : The mean change at week 12 from baseline in CPL409116 at dose of 240 mg BID is the same as that observed in placebo arm.

H_A3 : The mean change at week 12 from baseline in CPL409116 at dose of 240 mg BID is different from that observed in the placebo arm.

These hypotheses will be tested using a 2-sided 5% significance level. No adjustment for multiplicity will be performed for comparisons of each concentration of CPL409116 to placebo at week 12.

Primary endpoint, change from Baseline in Disease Activity Score DAS28-CRP at Week 12, will be analyzed by MMRM model with factors for dose (placebo, 60 mg, 120 mg, 240 mg), timepoint (all measurements throughout the study will be taken into account, week 4, week 8, week 12, week 16), interaction between treatment and timepoint, clinical site, as well as baseline value of DAS28-CRP as continuous covariate. Subject will be treated as a random effect, with an unstructured covariance structure to account for the correlation among repeated measurements. If the model does not converge, another covariance structure, (e.g., AR(1), CS, etc.) will be explored. Missing data will be assumed to be missing at random. R formula which could be used for such analysis:

$$mmrm(CHANGE \sim TREATMENT * TIMEPOINT + AGE + SEX + SITE + BASELINE + us(VISIT|ID))$$

using *mmrm* function from *mmrm* library.

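### No patient-reported secondary endpoint gets an estimated difference from placebo as its own endpoint, although the physician's global score and joint counts in the same section get the primary-type MMRM

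*SAP*

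**What the plan says.** The SAP's list of secondary endpoints (2.1.2) includes PAAP, PtGA and HAQ-DI at Weeks 4, 8 and 12, for example "Change from baseline in the Health Assessment Questionnaire – Disability Index (HAQ-DI) at Week 4, 8, and 12". It also includes the eight SF-36 domains, the physical and mental component scores, and the FACIT-F total at Week 12. The first secondary efficacy objective (SAP 2.1.2, Secondary objectives) is "To determine the effect of CPL409116 at 3 different doses, compared to placebo in subjects with rheumatoid arthritis".

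For the analysis, SAP 4.11.2 says that the changes in all five of these instruments "will be only presented descriptively for each timepoint". Protocol 10.9 says that these changes "will be presented descriptively for each timepoint. Description of additional analyses will be provided in the SAP". SAP 4.3 puts summary tables by randomised arm.

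The same section of the SAP treats other continuous secondary endpoints differently: tender and swollen joint counts "as well as change from baseline in PhGA will be analyzed using MMRM and performed as described for primary endpoint". That model (SAP 4.11.1) carries treatment, timepoint, their interaction and site, "as well as baseline value of DAS28-CRP as continuous covariate", and yields LS means with 95% CIs and p values for each dose against placebo.

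On missing data, SAP 4.6 analyses the main populations as observed, with LOCF as a sensitivity analysis for continuous endpoints. SAP 4.11.2 adds a PP repeat.

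**The concern.** A table of arm means does not estimate an effect compared with placebo. Readers will compare mean changes across four arms by eye, without an interval to show how uncertain each difference is.

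The treatment is also uneven. The physician's global score is modelled; the patient's global score, pain and HAQ-DI, due at the same Weeks 4, 8 and 12, are not. The SAP gives no reason. Multiplicity cannot be the stated one, because SAP 4.11.2 plans no correction for secondary endpoints and still reports p values for remission and for four ACR thresholds.

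Two statistical features are lost. First, change from baseline subtracts the baseline but does not adjust for it as a covariate, and arms of about 25 are open to chance imbalance. Second, a Week 12 as-observed mean covers only patients with a Week 12 value, whereas the MMRM would also use the earlier visits under missing at random. A patient who stops treatment leaves the trial (Protocol 7.2), and 16% drop-out is assumed (SAP 2.3).

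**Working it through.** **Is a stand-alone contrast planned anywhere?** I looked at each place where one could be:

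- SAP 4.11.2: descriptive only for all five instruments.
- Protocol 10.9: descriptive, with any additional analyses left to the SAP.
- SAP 4.11 and 4.11.2: PP, LOCF-imputed and subgroup repeats. For these scales they repeat descriptive tables.
- SAP 4.18: DAS28-ESR, DAS28-CRP response category, remission against ACR, and further subgroups. No model for a patient-reported scale is named.
- SAP 4.2.13: PtGA, PAAP and HAQ-DI are three of the five remaining ACR core measures, so they are compared with placebo inside a responder composite. SF-36 and FACIT-F are not in it.

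No section plans one.

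**Which model fits the data collected?** PAAP, PtGA and HAQ-DI have several post-baseline visits, so the MMRM applies directly. By footnote cc to SAP Table 1, SF-36 and FACIT-F have only Days 85 and 113 after baseline (plus early withdrawal). A Week 12 ANCOVA suits those.

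**What would covariate adjustment gain?** The documents give no figure for these scales. The only sample-size arithmetic is for the primary endpoint: 84/(1 − 0.16) = 100, so 25 per arm enrolled and 21 evaluable, which reproduces. For precision, let s0 and s1 be the baseline and Week 12 SDs and r their correlation. The correlation is assumed, because none is given.

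- Variance of raw change: s0² + s1² − 2·r·s0·s1
- Variance after baseline adjustment: s1²·(1 − r²)
- With s0 = s1 the ratio is (1 − r²)/(2(1 − r)) = (1 + r)/2

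The only SD pair in the documents is for DAS28-CRP (SAP 2.3): s0 = 1.0, s1 = 1.1. It serves here as an illustration of unequal SDs.

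| r (assumed) | Ratio, equal SDs | Reduction | Raw change, SDs 1.0/1.1 | Adjusted, SDs 1.0/1.1 | Ratio | Reduction |
|---|---|---|---|---|---|---|
| 0.3 | 0.65 | 35% | 2.21 − 0.66 = 1.55 | 1.21 × 0.91 = 1.101 | 0.71 | 29% |
| 0.5 | 0.75 | 25% | 2.21 − 1.10 = 1.11 | 1.21 × 0.75 = 0.9075 | 0.82 | 18% |
| 0.7 | 0.85 | 15% | 2.21 − 1.54 = 0.67 | 1.21 × 0.51 = 0.617 | 0.92 | 8% |

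**How precise would a difference from placebo be?** The 95% half-width is 1.96 × SD × √(2/n), in units of the score SD with equal SDs, where SD is √(1 − r²) adjusted and √(2(1 − r)) unadjusted.

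| n per arm | Adjusted, r = 0.3 / 0.5 / 0.7 | Unadjusted change, r = 0.3 / 0.5 / 0.7 |
|---|---|---|
| 25 | 0.53 / 0.48 / 0.40 | 0.66 / 0.55 / 0.43 |
| 21 | 0.58 / 0.52 / 0.43 | 0.72 / 0.60 / 0.47 |

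**How many contrasts would be added?** Four scores (PAAP, PtGA, HAQ-DI, FACIT-F total), eight SF-36 domains and two component scores make 14. Then 14 × 3 doses = 42 at Week 12, and 42 × 0.05 = 2.1 expected to be nominally significant if no dose had any effect.

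**The case against.** The strongest reply is that this is a deliberate, pre-specified choice. Protocol and SAP say the same thing, and the protocol's reference to additional analyses permits them without requiring them. The objective names no endpoint and does not promise inference on every scale. Placebo comparisons are already planned for DAS28-CRP, remission, time to remission, joint counts, PhGA and four ACR thresholds. Patient-reported information enters the ACR rates, and a disease-activity VAS enters DAS28-CRP (Protocol 8.4). With about 25 per arm and 42 correlated contrasts, describing these scales is a defensible phase II decision.

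Most of this stands, and it limits the point to a gap in supportive secondary analyses. It does not remove the gap. A composite cannot show whether pain or function improved by itself, and it says nothing about SF-36 or FACIT-F. The number of contrasts argues for labelling the results as estimates. It does not explain why the physician's score is modelled and the patient's is not.

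A reader might go further and infer that the planned summaries ignore baseline and drop-out. The documents do not support that: the summaries are changes from baseline, SAP 4.3 reports N and the number missing, and LOCF and PP repeats are planned. What is missing is covariate adjustment and a missing-at-random analysis. A reader might also take the variance reductions as efficiency lost in a planned test. They are not, because no change-score contrast is planned either.

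**Conclusion.** The point holds as a limitation of the secondary analyses. No patient-reported scale gets a difference from placebo with an interval as its own endpoint, and SF-36 and FACIT-F enter no comparison at all. Baseline is subtracted but not used as a covariate, and drop-out is handled only by LOCF and PP repeats of descriptive tables.

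It would be wrong to infer that the SAP departs from the protocol or that the primary result is at risk.

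The finding rests on the text and needs no assumption. The size of the gain does: the correlations are assumed, the 35%, 25% and 15% need equal SDs, and the 29%, 18% and 8% borrow the DAS28-CRP SDs. Adding the analyses is an improvement worth making, not a condition for a valid trial.

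**What to change.** Before unblinding, amend SAP 4.11.2 as follows:

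- Analyse PAAP, PtGA and HAQ-DI with the primary-type MMRM, with each scale's own baseline as the covariate. State this explicitly, because the primary model names the DAS28-CRP baseline.
- Analyse the Week 12 FACIT-F total, SF-36 domain scores, PCS and MCS by ANCOVA with treatment, site and the scale's own baseline.
- Report LS-mean differences of each dose from placebo with 95% CIs, labelled as supportive estimates not adjusted for multiplicity. Keep the descriptive tables.

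No extra patients, visits or data are needed, and the MMRM and LS-means code is already planned. The cost is interpretive: up to 42 Week 12 contrasts, about 2 of them nominally significant by chance at 5%. By default SAP 4.11 would repeat them in the PP and imputed ITT populations (42 × 3 = 126) and again in subgroups, so the amendment should say which of those repeats apply.

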Statistical Methods	
Statistic Considerations
 
Following assumptions have been made for the purpose of sample size determination:
 

■ CPL409116 molecule study will be based on four parallel study arms (placebo and three increasing doses of CPL409116);

■ No interim analyses for efficacy are planned;

■ Subject with active rheumatoid arthritis (Baseline DAS28>3.2)

■ Study is performed in a multiple clinical sites;

■ Primary objective is considered: Change from Baseline in Disease Activity Score (DAS)28-C Reactive protein (CRP) (Week 12);

■ The primary endpoint will be analyzed using a mixed effect repeated measures model (MRMM). However, to estimate sample size a simulation based on ANCOVA model was used. This should be more conservative (i.e. should underestimate statistical power) than MRMM but allows for more robust sample size estimation;

■ Analyses for each dose will take form of ANCOVA model with Baseline DAS28-CRP, clinical site (up to five sites were considered in simulation) and drug dose (encoded as levels 1-3) as independent variable;

■ for both endpoints a normal distribution of baseline and final values is assumed;

■ in the scenario single ANCOVA model will be performed at the end of the study. Study is successful if at least one

	
treatment arm is superior to placebo.
 
Eighty four subjects (21 per treatment group) are required to have a 80% chance of detecting, as significant at the 5% level, a mean change in DAS28-CRP of -1.8 provided that change no greater than -1.0 will be observed in placebo group with combined standard deviation of 1.1. With dropout of ~16% - 100 subjects should be recruited, which gives 25 subject in each treatment group.

--	--

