2.2. Study design

This is a 12-week, phase II, multicentre, randomised, double blind, efficacy and safety study of CPL409116 in participants with active rheumatoid arthritis who are taking methotrexate but have an inadequate response to this drug.

Approximately 100 male and female subjects are to be enrolled in the study. Eligible subjects are to be randomized into one of the 4 treatment arms determined in points below:

- 25 are to be randomized to the treatment arm with CPL409116 at a dose of 60 mg BID;
- 25 are to be randomized to the treatment arm with CPL409116 at a dose of 120 mg BID;
- 25 to the treatment arm with CPL409116 at a dose of 240 mg BID;
- 25 to the treatment arm with placebo.

Randomisation ratio is to be: 1:1:1:1. This will be the age-stratified randomisation. In all treatment arms investigated product/ placebo is to be administered orally for 12 weeks in a blinded fashion. In order to maintain the blind and minimize bias, all subjects will receive the same number and types of tablets each day of treatment.

The study consists of 3 phases:

- A Screening phase of up to 4 weeks,
- A double-blind treatment phase (Day 1 to Day 85/86; 12 weeks) with two doses of IMP administration per day (except Day 85 when patients are to ingest only one dose of IMP in the morning and except Day 86 without administration of CPL409116, when the last sample of blood will be collected for PK analysis in the morning),
- A 4 weeks post-treatment follow-up phase up to Week 16 (Day 113). Patients are to come to a study centre two times after the last dose of IMP. According to the schedule assessment in the follow-up period are planned two ambulatory visits and phone calls from clinical centres: Week 14 and 16 (Day 99 and 113 respectively)- an ambulatory visit; Week 13 and 15 (Day 92 and 106 respectively)- phone call from a clinical centre. The end of the study is planned at Week 16 (Day 113).

[figure not shown]

Figure 1. Study design

In the **Screening Period**, patients undergo screening assessments from Day -28 to Day 0. Rolling admission is employed in this study. Patients that fulfil all the inclusion criteria and none of the exclusion criteria will be considered eligible for this study. Subjects must complete all screening procedures and assessments and have test results available prior to the Baseline visit (Visit 2).

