2.3. Sample size

Sample size calculation for a trial with a continuous outcome measure defined as change from baseline was determined based on simulation of analysis of covariance (ANCOVA) where the baseline measure, treatment and clinical site are included as covariates in the analysis. The value assumptions were adopted from a published data. The outcome measure DAS28-CRP, measured at baseline and at 12-week postintervention. A decrease in the DAS28-CRP score indicates an improvement in health status. Assuming the baseline mean scores are the same for drug and placebo arms and equal to 5.5 (with standard deviation equal to 1.0). We assume 12-week mean score for drug equal to 3.7 (SD = 1.1) and for placebo 4.5 (SD = 1.1). With 21 patients per group, the study has >80% power to detect a difference of 0.8 points or greater compared to placebo, given 5% significance level. Assuming a 16% dropout rate the study will enroll approximately 100 subjects.

3. General aspects of the statistical analysis

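### The logistic models for remission and ACR response use placebo as reference in arms of about 25, with no rule for a placebo arm without responders; on the plan's figures that arm has no Week 12 remitter in 34% to 41% of trials

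*SAP*

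**What the plan says.** SAP 4.11.2 covers two groups of binary efficacy endpoints.

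- **Remission.** "Proportion of subjects with DAS28-CRP remission (score < 2.6) in each study arm will be presented at any time", and also at Days 29, 57, 85 and 113. Each arm is compared with placebo by a proportion test, with a confidence interval for the difference. The logistic model is for response at any time, with treatment (placebo as reference), country and baseline DAS28-CRP.
- **ACR20/50/70/90.** "Difference between CPL409116 arms and placebo will be presented together with confidence interval and p value calculated using proportion test". For the model: "Logistic regression model will be prepared similar to the previously described endpoint of DAS28-CRP remission".

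SAP 4.11 and 3.2 repeat the efficacy analyses by age, sex and baseline severity. Allocation is equal ("Randomisation ratio is to be: 1:1:1:1"), with 25 patients planned per arm.

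The SAP does not say whether the proportion test uses a continuity correction, which interval is used for a difference between arms in efficacy, or what happens to the logistic model if an arm has no responders. It does name methods elsewhere: Wilson intervals for single-arm ACR rates, Agresti-Caffo intervals for adverse-event differences, and alternative covariance structures if the primary repeated-measures model does not converge.

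Protocol 10.3 also plans logistic models with treatment and baseline DAS28-CRP. Its remission model follows the sentence on Week 12 remission and adjusts for clinical site rather than country.

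**The concern.** Placebo is the reference level, so every dose odds ratio depends on the placebo odds. If no placebo patient responds, those odds are estimated as zero and all three dose coefficients diverge together. Software then usually prints a very large number with a huge standard error, from which a Wald interval and p-value mean nothing.

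Placebo remission is plausibly rare in this design, and the subgroup repeats reduce the counts further. If the remedy is chosen after unblinding, the choice of method, and of test variant, is made with the results in view. A ready-made small-sample method exists and could be named now.

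**Working it through.** **Inputs**
- Week 12 DAS28-CRP: drug mean 3.7, placebo mean 4.5, SD 1.1 in each (SAP 2.3).
- Distribution: "for both endpoints a normal distribution of baseline and final values is assumed" (Protocol 1.1, Statistical Methods).
- Remission: score below 2.6 (SAP 4.11.2).
- Arm size: 25 randomised. With 21 evaluable per arm and 16% dropout, 84 / 0.84 = 100, or 25 per arm, which reproduces the plan's figure. SAP 4.6 analyses data as observed in the main analysis, so about 21 per arm is the relevant number at Week 12.

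**Implied Week 12 remission**
- Placebo: Φ((2.6 − 4.5)/1.1) = Φ(−1.727) = 4.2%, or 1.05 expected remitters in 25.
- Drug: Φ((2.6 − 3.7)/1.1) = Φ(−1.0) = 15.9%, or 3.97 expected in 25.

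**Probability of no placebo remitter at Week 12**, (1 − 0.0421)^n
- n = 25: 34.2%.
- n = 21: 40.6%.
- n = 12: 59.7%, for a subgroup holding half the placebo arm (an even split is assumed).
- Range over the assumed SD, n = 25: 48% at SD 1.0 and 15% at SD 1.3.

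A drug arm can also be empty, with probability 1.3% (n = 25) or 2.7% (n = 21) per arm. The chance that at least one of the four arms is empty is 1 − (1 − 0.342)(1 − 0.0133)³ = 36.8% with 25 per arm, and 45.2% with 21.

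**The SAP's any-time outcome.** A Week 12 remitter is also an any-time remitter, so the zero-event probability cannot exceed the Week 12 figure. The plan gives no means or correlations for the other visits. As an illustration, the score was taken as normal at Weeks 4, 8, 12 and 16 with SD 1.1. Placebo means were either flat at 4.5, falling through 5.1, 4.8 and 4.5 to 4.5, or falling likewise and then rising to 5.0 at Week 16. Between-visit correlations were 0.5 to 0.9. The probability of no placebo remitter at any visit is then about 4% to 28% with 25 patients, and 6% to 34% with 21.

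**Effect of an empty placebo cell: 0/25 versus 4/25**
- Maximum-likelihood odds ratio: infinite.
- Firth estimate without covariates (0.5 added to each cell): (4.5/21.5)/(0.5/25.5) = 10.7.
- Proportion test, pooled rate 0.08, standard error √(0.08 × 0.92 × 2/25) = 0.0767. Uncorrected: z = 0.16/0.0767 = 2.09, p = 0.037. Corrected: z = (0.16 − 0.04)/0.0767 = 1.56, p = 0.118.

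**Exact behaviour of the two test variants**, 25 per arm, nominal two-sided 5%

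| | Uncorrected | Corrected |
|---|---|---|
| Power, 4.2% v 15.9% | 28% | 8% |
| Type I error, both 4.2% | 1.4% | 0.03% |
| Type I error, both 15.9% | 5.5% | 1.3% |
| Type I error, both 50% | 6.5% | 3.3% |

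**The case against.** A reader might infer that the odds ratios will fail to exist in one trial in three. The documents do not support that for the SAP's own model. Its outcome is response at any time over four visits, so the Week 12 figure is only a ceiling there, and the illustrative values are lower. That objection stands. The figure does apply to the Day 85 proportion comparison and to a Week 12 logistic model as in Protocol 10.3.

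A reader might also infer that all these outcomes are rare. The plan's figures show this only for placebo remission. Implied drug remission is about 16%, and no ACR rate is given, so nothing can be computed for ACR70 or ACR90.

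Third, a reader might take the 8% power as the plan's own. The SAP names R but no function and no continuity correction, so the uncorrected test is an equally permitted reading. What is established is that the variant is unstated and can change the result. Nor does the uncorrected test cure low power: with 21 per arm it is still only 22%.

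Finally, most planned outputs survive an empty placebo arm: arm proportions, differences from placebo, Kaplan-Meier summaries and the log-rank test. The endpoints are secondary and the primary analysis is untouched. All of this limits the size of the point. None of it supplies a rule for separation.

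**Conclusion.** The point holds as a cheap improvement to secondary analyses. In any trial or subgroup with no placebo responder, the logistic models as planned give infinite dose odds ratios with unusable Wald intervals and p-values.

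For Week 12 remission the chance of this is 34% with 25 placebo patients, 41% with 21, and about 60% in a subgroup of 12. These values rest on the plan's mean, SD and normality, and on an assumed even split for the subgroup. They are sensitive to the SD. For the SAP's any-time model they are upper bounds, and for ACR no rate can be derived.

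The choice of proportion test is a separate, smaller matter. At placebo-like rates neither variant inflates type I error. Preferring the uncorrected one is a trade-off, because its type I error rises to about 6.5% when rates are near 50%.

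**What to change.** In SAP 4.11.2, before unblinding:

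1. Specify Firth penalised logistic regression with profile-likelihood intervals for all binary efficacy models, including those in subgroups.
2. Name a score-type interval (Newcombe or Miettinen-Nurminen) for differences from placebo in remission and ACR response.
3. State which proportion test is used and whether a continuity correction applies.
4. Reconcile the remission model with Protocol 10.3 (any time with country, or Week 12 with site), so that it is clear which outcome the odds ratios describe.

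The cost is SAP wording and a little programming with standard R packages. Data collection and sample size do not change. Firth estimates shrink odds ratios slightly. If the uncorrected test is chosen, the SAP should acknowledge that its exact type I error with 25 per arm can reach about 6.5%, which could matter for ACR20 if response is common.
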